3.1.3 Tertiary objectives and endpoints

[REDACTED]	[REDACTED]

3.2 Design of the clinical trial

This is a multicentre, first in human (FIH), open label dose escalation trial, Phase I/IIa study in patients with B-cell malignancies. The clinical trial is in two parts (see Figure 2);

Part A: The first part of the study will be a dose escalation stage conducted in two arms:

- **Arm 1 (single agent):** Dose escalation phase to determine the MTD or MAD and recommended Phase II dose (RP2D) for evaluation of BI-1206 as a single agent.
- **Arm 2 (combination):** Dose escalation phase to determine the MTD or MAD and RP2D of BI-1206 administered in combination with an anti-CD20 antibody. Rituximab has been chosen as the most appropriate anti-CD20 antibody (see Sections 2.2.6 and 2.2.7).

Part B: The second part of the study will be a dose expansion stage conducted in two arms:

[figure not shown]
- **Arm 1 (single agent):** Expansion cohort of up to 25 patients with CD32b+ B-cell malignancies administered single agent BI-1206 at the RP2D as determined in Part A, Arm 1. This expansion will include a minimum of 12 chronic lymphocytic leukaemia (CLL) and 6 mantle cell lymphoma (MCL) patients.
Part B, Arm 1 will be able to open once a RP2D in Part A Arm 1 is established.
- **Arm 2 (combination):** Expansion cohort of up to 25 patients with CD32b+ and CD20+ B-cell malignancies at the RP2D that can be given with an anti-CD20 antibody as determined in Part A. This expansion will include a minimum of 12 CLL and 6 MCL patients.
Part B, Arm 2 will be able to open once a RP2D in Part A Arm 2 is established.

In both Parts A and B, if a patient shows evidence of clinical benefit (as defined in Section 10.2), they will be eligible to continue on maintenance therapy. Maintenance therapy will consist of a single dose of BI-1206 \pm rituximab every eight weeks for up to one year after Week 1 of induction therapy.

It is expected that up to 81 evaluable patients will be required to complete this trial, with the final number depending on the number of dose levels explored.

Figure 2: Schematic of trial design

Boxes outlined in red are those to which the DLT definition described in Section 3.3 applies.

3.3 Definition of dose limiting toxicity

Some of the dose limiting toxicity (DLT) and maximum tolerated dose (MTD) definitions are derived from the National Cancer Institute (NCI) Common Terminology Criteria for Adverse Events (CTCAE) Version 4.02. Please note that not all of the events described as DLTs are fully supported by NCI CTCAE but are formed by amalgams of different events in order to assist with assessments of adverse events.

The definition of DLT applies to both the single agent and combination dose escalation arms (Part A of the study [boxes outlined in red in Figure 2]).

A DLT is defined as a highly probably or probably **BI-1206 or rituximab-related AE occurring during** the four weeks of induction treatment and up to one week post the fourth infusion of BI-1206 (i.e. by Day 28/Week 5) which fulfils one or more of the following criteria:

- Neutropenia or neutrophil count decrease Grade 4 ($ANC < 0.5 \times 10^9/L$) for >10 days duration
*see note despite growth factor support
- Febrile neutropenia (fever of unknown origin without clinically or microbiologically documented infection) with Grade 3 or 4 neutropenia (absolute neutrophil count [ANC] $<1.0 \times 10^9/L$) and fever $\geq 38.5^\circ C$).
- Infection (documented clinically or microbiologically) with Grade 3 or 4 neutropenia ($ANC < 1.0 \times 10^9/L$)
- Thrombocytopenia or platelet count decrease Grade 4: a) for ≥ 5 days*see note, or b) associated with active bleeding, or c) requiring platelet infusion
- Grade 3 or 4 non-haematological toxicity. This includes Grade 3 and 4 biochemical AEs as DLTs.

EXCLUDING:

- Grade 3 or 4 nausea or vomiting in patients who have not received optimal treatment with anti-emetics
- Grade 3 or 4 diarrhoea in patients who have not received optimal treatment with anti-diarrhoeals
- Alopecia
- Grade 3 infusion related reactions
- Transient, asymptomatic Grade 3 biochemical abnormalities if agreed by the Sponsor and the study team, including the Chief Investigator
- Event with a fatal outcome.

***Note: In the event of a Grade 4 neutropenia or Grade 4 thrombocytopenia, a full blood count must be performed at least on Day 10 (Day 5 for thrombocytopenia) after the onset of the event to determine if a DLT has occurred. The investigator must continue to monitor the patient closely until resolution to Grade 3 or less. Please See [Section 5.9.4](#) 'Management of thrombocytopenia (Grade 4)' for further details.**

Refer to Section 5.3 for detail concerning intra-patient dose escalation and DLT.

DLTs defined above will be considered for the purposes of dose escalation decisions; however, should cumulative toxicity become apparent this will also be taken into consideration when determining either the next dose level or the RP2D

Should any change be made to the grade or causality of an AE during the trial that may alter its DLT status, the Sponsor must be informed immediately as this may affect dose escalation decisions.

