3 TRIAL DESIGN

3.1 Clinical trial objectives and endpoints

3.1.1 Primary objectives and endpoints

Primary objectives	Endpoints
Part A Escalation phase	
Arm 1: To propose a recommended dose for Phase II evaluation of BI-1206 as a single agent in by:	
(a) Establishing the maximum tolerated dose (MTD) or maximum administered dose (MAD) of BI-1206 given once weekly for four weeks, via intravenous infusion in patients with relapsed or refractory B-cell malignancies in Part A only.	(a) Determining the maximal dose (up to 800 mg) of BI-1206 at which no more than one patient out of up to six patients at the same dose level experience a highly probably or probably BI-1206 related dose-limiting toxicity during induction therapy and up to one week post the fourth infusion.
(b) Assessing the safety and toxicity profile of BI-1206 as a single agent in Part A and Part B	(b) Documenting adverse events (AEs), serious adverse events (SAEs) (graded according to NCI-CTCAE Version 4.02) and laboratory parameters and determining their causality in relation to BI-1206. Causality of AEs/SAEs will be assessed by the Investigator.
Arm 2: To propose a recommended dose for Phase II evaluation of BI-1206 in combination with an anti-CD20 antibody by:	
(c) Establishing the MTD or maximum administered dose MAD of BI-1206 and an anti-CD20 antibody given once weekly for four weeks, via intravenous infusion in patients with relapsed or refractory B-cell malignancies in Part A only.	(c) Determining the maximal dose (up to 800 mg) of BI-1206 at which no more than one patient out of up to six patients at the same dose level experience a highly probably or probably BI-1206 or anti-CD20 antibody-related dose-limiting toxicity during induction therapy and up to one week post the fourth infusion.
(d) Assessing the safety and toxicity profile of BI-1206 in combination with an anti-CD20 antibody in Part A and B.	(d) Documenting AEs, SAEs (graded according to NCI-CTCAE Version 4.02) and laboratory parameters and determining their causality in relation to BI-1206 and, where appropriate, anti-CD20 antibody. Causality of AEs/SAEs will be assessed by the Investigator.
Part B Expansion phase	

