3.5.4 Combination dose escalation decisions (Part A, Arm 2)

The starting dose for BI-1206 in Part A, Arm 2 will not exceed the highest dose of single agent of BI-1206 that has been safely administered in Part A, Arm 1 (at the time of opening Part A, Arm 2), and which is deemed clinically appropriate to combine with rituximab. The starting dose in Part A, Arm 2 will be determined at a dose decision meeting following review of a completed cohort in Part A, Arm 1.

Once Arm 2 is opened, patients treated in the combination dose escalation cohorts who either receive four administrations of BI-1206 in combination with rituximab or experience a DLT will be evaluable for dose escalation and/or cohort expansion decisions in Part A, Arm 2.

Patients who receive less than 80% of their total planned induction doses (total across the four administrations) but complete the DLT period (Week 5) are not evaluable for dose escalation decisions (unless they have experienced a DLT).

Data from all patients who receive less than 4 doses of BI-1206 in combination with rituximab and available data from Part A, Arm 1 will also be reviewed and taken into consideration for subsequent dose escalations in the combination arm. Data from any other trials investigating BI-1206 will also be considered in the dose escalation decisions.

For patients who do not receive the total full dose, please see [Section 5.9.6](#) 'Dose delays/treatment discontinuation' which also offers guidance on the thresholds for re-challenging patients post related AE observation.

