BI-1206 and rituximab will each be administered once weekly for four weeks via separate IV infusions. Based on the proposed mechanism of action of BI-1206 binding to the CD32b receptor and blocking its ability to internalise rituximab, BI-1206 will be administered prior to rituximab. The timeframe within which the two infusions can be given (i.e. on the same day or on subsequent days) will be determined by the length of each infusion. At Week 1 both infusions will be administered over a longer period of time as a precautionary measure and so the BI-1206 dose will be given on Day 1 and the rituximab dose on Day 2. In subsequent weeks, if patients have not experienced a significant infusion reaction at Week 1 then the BI-1206 and rituximab infusions can be given at a faster rate. Therefore, from Week 2 onwards, if the infusion times allow, the doses of BI-1206 and rituximab may be given on the same day. BI-1206 will be given prior to rituximab on all occasions. If infusion times are not compatible with same-day dosing, administration of BI-1206 and rituximab on subsequent days will continue. These cohorts will include a minimum of one patient as described in Section 5.5.

Patients who show clinical benefit at eight weeks (as defined in Section 10.2) will move to a maintenance phase of treatment (refer to Section 5.2.5).

Figure 3: Combination dosing schedule during induction therapy

	Week 1				Week 2				Week 3				Week 4			
	D1	D2	D3	D4	D8	D9	D10	D11	D15	D16	D17	D18	D22	D23	D24	D25
BI-1206	X				X				X				X			
Rituximab			X		X ¹				X ¹				X ¹			

¹ Rituximab may be given on Day 1 following BI-1206 from Week 2 onwards if no significant infusion reaction has been observed at Week 1 and if infusion times allow this.

Otherwise it will be given on Day 2 as in Week 1.

5.2.3 Dosing schedule/treatment schedule in BI-1206 single agent expansion phase (Part B, Arm 1)

BI-1206 will be administered once weekly for four weeks via IV infusion at the RP2D as defined by Part A, Arm 1 this will be classified as induction therapy; refer to Section 5.7. Patients with clinical benefit (as defined in Section 10.2) at eight weeks will move to a maintenance phase of treatment as described in Section 5.2.5.

5.2.4 Dosing schedule/treatment schedule in BI-1206/rituximab combination expansion phase (Part B, Arm 2)

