- The decision to expand a minimum of one patient cohort to a 3+3 cohort following a clinically relevant \geq Grade 2 related toxicity will be documented and distributed by the Sponsor to all Investigators as per Section 5.3.4. The decision may occur outside the dose decision meetings as it is dependent on when the event/s occurs. The assessment of a clinically relevant toxicity will end at Week 5 (same as the DLT period i.e. one week post fourth infusion).
- As per Section 9.4, related toxicity will be highly probably, probably and possibly related to BI-1206 (or rituximab in Arm 2).

It should be noted that dose escalation and cohort size decisions will be made based on data from completed cohorts in the single agent arm (Arm 1); available data from the combination arm (Arm 2) will be also be reviewed and considered in the Arm 1 dose decision meetings. Please refer to Section 5.3 for details of the communication plan, the process for dose escalation review and decision making and the dissemination of information.

All patients in a cohort must have completed induction therapy and 7 days post the fourth infusion for dose-escalation to the next cohort to occur. The second patient in any cohort will not commence treatment until after the first patient in that cohort has completed two infusions of BI-1206; the third patient in any cohort will not commence treatment until after the second patient in that cohort has completed one infusion of BI-1206.

Figure 4: Dose escalation decision-making and action if clinically relevant \geq Grade 2 related toxicity and/ or DLT observed at dose levels from Cohort 2 (Part A, Arm 1)

dx = initial dose level dx +1 = 1 level above initial dose

5.4.3 Dose escalation and action if a DLT observed at dose levels from Cohort 2 onwards, Part A, Arm 1

If one instance of DLT is observed in any cohort, the cohort will be expanded to include up to six patients. If one out of the six patients experience a DLT then dose escalation will continue, and the next cohort will consist of a minimum of 3 patients as described in Figure 4. If no DLTs are seen in 3 patients, further escalations will continue as 3+3 cohorts.

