5.5 BI-1206 and rituximab escalation cohorts (Part A, Arm 2)

The combination escalation arm (Part A, Arm 2) will open to recruitment following review of a completed single agent dose level in Arm 1. The starting dose for BI-1206 in combination with rituximab will be agreed at a dose decision meeting based on data from completed cohorts in the single agent arm. The combination dose will not exceed the highest dose of BI-1206 safely given (≤ 1 DLT in up to six patients) as a single agent to date and must be deemed clinically appropriate to combine with rituximab.

The dose(s) of rituximab will be 375 mg/m² based upon the approved dose of rituximab. For the purpose of this trial, all patients including CLL patients will receive 375 mg/m² for every rituximab infusion for consistency.

Once the combination escalation arm (Part A, Arm 2) is opened, it will run in parallel to the single agent escalation arm (Part A, Arm1) but dose decisions and cohort size decisions will be made independently for each arm. Combination cohorts will also be a minimum of one patient and dose escalation/cohort expansion decision-making as described in Sections 5.4.2 and 5.4.3 will also apply to the combination escalation cohorts.

It should be noted that dose escalation decisions will be based on data from the combination arm (Arm 2) with available data from the single agent arm (Arm 1) and any other ongoing trials with BI-1206 also being reviewed and considered. Please refer to Section 5.3 for details of the communication plan and process for dose escalation review and dissemination of information.

All patients in a cohort must have completed induction therapy and 7 days post the fourth infusion without DLT for dose-escalation to the next cohort to occur. The second patient in any cohort will not commence treatment until after the first patient in that cohort has completed two infusions of BI-1206 in combination with rituximab; the third patient in any cohort will not commence treatment until after the second patient in that cohort has completed one infusion of BI-1206 and rituximab.

In Part A, Arm 2 the dose level of rituximab will be fixed and the dose level of BI-1206 will be explored in the escalation phase in order to establish the BI-1206 MAD or MTD and RP2D in combination with rituximab, see Section 3.4.

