5.9 Dose modifications

Protocol defined dose modification criteria for treatment in Part B will be reviewed and updated if required based on the emerging clinical data from Part A of the trial.

For the combination arms in Parts 1 and 2, BI-1206 and rituximab should be administered independently of any dose delay to the other agent. The decision to continue with either agent alone, if the other has to be withdrawn, should be at the discretion of the investigator depending on whether there is clinical advantage to continuing with treatment.

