5.9.7 Duration of treatment

In the induction phase, treatment should continue for four weeks unless (a) the patient asks to be withdrawn, (b) there is evidence of disease progression, (c) the patient is experiencing unacceptable toxicity or (d) the Investigator feels the patient should be withdrawn for any other reason. Other reasons are listed in Section 11.

The duration of treatment may be extended if dose interruptions/ delays result in an extended induction period.

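### In the combination escalation arm, the DLT window is timed on BI-1206 alone, so a rituximab-related event after a late fourth rituximab dose may not be counted

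*Combined protocol and SAP*

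**What the plan says.** Section 3.3 applies one DLT definition to both escalation arms and attributes events to BI-1206 or rituximab. The window covers the four weeks of induction and runs "up to one week post the fourth infusion of BI-1206 (i.e. by Day 28/Week 5". No rituximab date enters it.

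Other sections bear on the same window:

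- **3.1.1, endpoint (c)** counts a "BI-1206 or anti-CD20 antibody-related dose-limiting toxicity during induction therapy and up to one week post the fourth infusion" and names no agent for that infusion.
- **3.5.4** says that Arm 2 patients who "either receive four administrations of BI-1206 in combination with rituximab or experience a DLT will be evaluable" for escalation decisions. It also places the end of the DLT period at Week 5, and asks for no observation time after the last rituximab dose.
- **5.4.2**, applied to Arm 2 by 5.5, gives the Grade 2 or higher cohort-expansion trigger: "The assessment of a clinically relevant toxicity will end at Week 5 (same as the DLT period i.e. one week post fourth infusion".
- **5.5** says that all patients in a cohort "must have completed induction therapy and 7 days post the fourth infusion without DLT for dose-escalation" to the next cohort. Again no agent is named.
- **5.2.2** sets the Week 1 schedule: "the BI-1206 dose will be given on Day 1 and the rituximab dose on Day 2". From Week 2 rituximab is given on the same day if there was no significant infusion reaction and infusion times allow, and otherwise on the next day.
- **5.9** says that "BI-1206 and rituximab should be administered independently of any dose delay to the other agent", and **5.9.7** adds: "The duration of treatment may be extended if dose interruptions/ delays result in an extended induction period".
- **5.9.6** allows a logistical delay of at most one week, agreed by the Chief Investigator and Sponsor.

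**The concern.** Attribution covers two drugs, but the clock follows one. While the two antibodies stay together this hardly matters. Once rituximab falls behind, the last part of the combination exposure is observed for less time than intended, or not at all, for DLT purposes.

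The combination MTD is a primary endpoint decided by DLT counts: two DLTs in up to six patients define the maximum administered dose (3.4.1, carried to Arm 2 by 3.4.2). Arm 2 cohorts can be as small as one patient, and the trigger that would enlarge such a cohort closes at the same time as the DLT window. If the lagged patient is still evaluable, the denominator keeps the patient while the numerator can lose the event, which favours escalation.

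**Working it through.** **1. The plan's own date.** BI-1206 is given on Days 1, 8, 15 and 22 (5.2.2, Figure 3). The window ends on Day 22 + 7 = Day 29, which is 28 elapsed days. The Day 28 in 3.3 is therefore reproduced as elapsed time; in Day 1 numbering it is Day 29, the day of the Week 5 visit in 7.6. Both ends are shown below.

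**2. Observation left after the fourth rituximab dose.** Let L be the lag in days carried to that dose. Next-day dosing puts it on Day 23 + L, leaving 6 − L days to Day 29 or 5 − L to Day 28. Same-day dosing puts it on Day 22 + L, leaving 7 − L or 6 − L. Negative values are set to 0.

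| Lag L | Next-day: dose day | Days left (to Day 29 / 28) | Same-day: dose day | Days left (to Day 29 / 28) |
|---|---|---|---|---|
| 0 | 23 | 6 / 5 | 22 | 7 / 6 |
| 3 | 26 | 3 / 2 | 25 | 4 / 3 |
| 5 | 28 | 1 / 0 | 27 | 2 / 1 |
| 7 | 30 | 0 / 0, dose outside window | 29 | 0 / 0 |

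Counting to Day 29, observation reaches zero at L = 6 (next-day) or L = 7 (same-day). On the Day 28 reading it does so one day sooner.

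**3. Which rules cover an event after that point.** Take rituximab on Days 2, 16, 23 and 30, with BI-1206 on time.

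- A qualifying rituximab-related event on Days 30 to 37 is outside 3.3.
- It is also outside the 5.4.2 trigger, which ended at Week 5.
- The 5.5 gate may delay escalation, but its condition is freedom from DLT, and this event is not a DLT.
- Treating induction as extended under 5.9.7 could cover events up to the late dose, but adds no follow-up after it.

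If one of six patients already had a DLT, the count stays at 1/6 under 3.3. It would be 2/6, the maximum administered dose, if endpoint (c) is taken to mean the later infusion.

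**4. Effect on the 3+3 rule (illustration).** Assumptions not in the documents: a true DLT probability p of 0.33 (range 0.25 to 0.40); one lagged, evaluable patient among the first three; risk spread equally over eight infusions. One infusion is unobserved, so that patient's observable probability is p × 7/8. As a variant, the late dose carries half the average risk, giving p × 15/16; section 2.2.6 says infusion-related symptoms fall with later infusions.

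Pass chance = P(0 of 3) + P(1 of 3) × P(0 of next 3). With no lag and p = 0.33: 0.67³ + 3(0.33)(0.67²)(0.67³) = 0.301 + 0.134 = 0.434. With one patient at 0.33 × 7/8 = 0.289, P(0 of 3) = 0.67² × 0.711 = 0.319 and P(1 of 3) = 0.444, so the pass chance is 0.319 + 0.444 × 0.301 = 0.453.

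| p | No lag | 7/8 | 15/16 |
|---|---|---|---|
| 0.25 | 0.600 | 0.615 | 0.607 |
| 0.33 | 0.434 | 0.453 | 0.444 |
| 0.40 | 0.309 | 0.329 | 0.319 |

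The shift is about 1 to 2 percentage points. In a one-patient cohort at p = 0.33, the chance of showing no DLT is 0.670 without a lag, 1 − 0.289 = 0.711 at 7/8, and 0.691 at 15/16.

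**The case against.** The case for leaving the text alone is substantial.

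- **The event would be seen.** Section 5.3.1 bases the decision on safety data from all patients in the cohort, at least 7 days after the fourth dose. Section 5.3.2 puts drug-related adverse events, late-arriving information and cumulative concerns on the agenda, and lets the meeting choose the next cohort's size. Section 5.3.3 requires approval by the Sponsor's Head of Medical Sciences. Sections 3.3 and 3.4.2 also allow cumulative toxicity and early stopping to be considered. This stands and limits the harm. But these are judgements, and they do not alter the count that defines the maximum administered dose.
- **A lagged patient may not be evaluable.** The 3.5.4 wording can mean paired administrations. In the example above, the Day 8 BI-1206 dose and the Day 30 rituximab dose have no partner, so only three pairs were given. On that reading the patient would have to be replaced and the bias towards escalation goes. The event is still not counted, because only a DLT would restore evaluability and 3.3 does not make it one.
- **BI-1206 is the drug being escalated.** Rituximab is fixed at 375 mg/m², Grade 3 infusion reactions are not DLTs, and rituximab reactions cluster at the first infusion (2.2.6). A late fourth rituximab dose is thus a weak source of information on the BI-1206 MTD. This is fair, but 3.3 chose to count rituximab-related events, and its window should match that choice.
- **The case is uncommon.** The text permits a rituximab-only delay without describing one. A logistical delay needs agreement and is capped at one week, and toxicity holds under 5.9.6 apply to both agents. The documents give no basis for a frequency.

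A reader might infer that any rituximab delay makes later events uncountable, or that patients on schedule are under-observed. The table in the working shows otherwise: short lags leave some window, and on-schedule dosing leaves 5 to 7 days.

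**Conclusion.** The mismatch is in the current text. In Arm 2, if the fourth rituximab dose lags by about 6 to 7 days or more, a qualifying rituximab-related event after it is not a DLT under 3.3, and the 5.4.2 trigger has closed as well. Shorter lags shorten the observation without removing it.

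The size is small: about 1 to 2 points on the 3+3 pass chance for one lagged patient, resting on assumed DLT rates and risk weights and on the reading of 3.5.4 that keeps the patient evaluable. The documents do not support a claim that escalation is certain to be biased, since evaluability is arguable, or that such events would go unnoticed, since the dose meetings review them. What remains is that the stated count can omit an event which the primary endpoint's wording could be taken to include. That is worth a low-cost correction, to be considered rather than required.

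**What to change.** For Arm 2, define the DLT window in 3.3 as ending 7 days after the later of the fourth BI-1206 and fourth rituximab infusions, and remove the Day 28/Week 5 parenthesis for that arm. Use the same wording in 3.1.1(c), in the follow-up requirement of 5.3.1, in the 5.5 gate, and for the end of the 5.4.2 trigger as applied to Arm 2.

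Optionally, say in 3.5.4 whether the 80% rule applies to each antibody separately. Four BI-1206 and three rituximab doses are 7/8 = 87.5% if pooled but 3/4 = 75% for rituximab alone. A patient who receives all four doses in full passes either way, so this is a side clarification.

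**Cost.** These are text edits, with no added patients. On-schedule patients would close on Day 29 (same-day, 22 + 7) or Day 30 (next-day, 23 + 7), within the Week 5 visit window of Day 29 (+3 days). A patient whose fourth rituximab dose is one week late would close on Day 36 or 37 and need one extra safety check, so that cohort's decision would wait about a week longer.
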